5.0 Sample and recruitment

5.1 Recruitment strategy

The study aims to recruit 20 adolescents with mild to moderate LD and clinical depression. A multi-point recruitment strategy¹⁹ will be adopted, involving primary health care services, specialist LD services, relevant voluntary organisations, local special schools, and parent carer groups (online and face-to-face). Self-referrals will also be accepted, as potential participants and carers may find out about the study through this multi-point recruitment strategy. Recruitment strategies will include outreach work with voluntary provider organisations to help them to identify adolescents with LD and depressive symptoms. Reviews will also be carried out with specialist health professionals to identify potential participants on caseloads who may be eligible. A record will be kept of the numbers of potential participants and individuals consenting to participate in the study, identified from each of these recruitment points.

5.2 Target Population

The research assistants will undertake consent/screening visits and check inclusion/exclusion criteria. During screening, the presence of a learning disability will be assessed using the Vineland Adaptive Behaviour Scale²⁰. The diagnosis of mild-moderate learning disability will be based on international criteria (ICD-10) that includes both low intellectual ability and adaptive behaviour deficits. Clinically significant depression will be defined by the Anxiety Disorders Interview Schedule for DSM-IV (Parent Interview Schedule)²¹.

5.3 Inclusion criteria:

1. Learning disability – a standard score in the range of 75 or below for the Adaptive Behaviour Composite score on the Vineland Adaptive Behaviour Scales 3rd edition

- 2. Adolescents identified administratively with a Learning Disability (LD), or with diagnostic information (IQ score below 70, assessed by a standardised test, and having deficits in adaptive functioning) age), and/or administratively defined as having LD (e.g., enrolled in a special school for children/adolescents with mild LD or in a SEN setting in a mainstream school, day centre etc)
- 3. Participants with LD may also have other conditions or developmental disabilities such as Autism Spectrum Disorder (ASD) or Attention deficit hyperactivity disorder (ADHD).
- 4. Participants with LD have capacity to assent/consent to take part in the research (and thus would then also have sufficient communication and understanding to take part in the treatment)
- 5. Aged 12-17 years
- 6. Clinically significant unipolar depression as determined using information gathered through clinical interview (ADIS).
- 7. Has support from a family member, or paid carer who can support them throughout the treatment.

5.4 Exclusion criteria:

- 1. A suicide attempt in the past six months; or require intensive (inpatient) treatment for mental illness
- 2. Intensive inpatient treatment for mental illness in the past 6 months
- 3. Anti-depressive medication initiated or changed dose in the past 4 weeks
- 4. Factors that prevent the young person from interacting with the supporter and therapist or retaining information from the therapy (e.g. severe psychosis, degenerative condition). Consent not given to contact the participant's GP about their participation in the study.
- 5. Currently receiving any psychological therapy for a mental health problem
- 6. Insufficient English language skills to complete the measures or participate in the treatment.

6.0 Recruitment Process

Procedures for participant recruitment are outlined in the following sections.

6.1 Informed consent

6.1.1 Participants

A study information leaflet will be given to potential participants, supported by a parent carer, by a member of staff known to the potential participant and working in primary health care services, specialist LD services, relevant voluntary organisations, special schools or directly to parent carer groups (online/face to face). The member of staff will give a brief explanation to the individual and their carer about the study and explain that they can contact the research team if they are interested in finding out more about the study.

Participant information sheets for use by adolescents with LD have been designed. These use language appropriate to the developmental level of individuals with a mild to moderate level of LD. A separate information sheet will be provided for their parent carer. When an individual is interested in finding out more about the study, a researcher will arrange to meet with them to discuss the study and answer any questions they have. It is anticipated that in the majority of cases, a researcher will meet the potential participant and their parent carer at their home. However, if this is not convenient or desirable for a potential participant and their parent carer, then they will be invited to identify an alternative place to meet. At the time of the first meeting with the potential participant and their parent carer, the researcher will invite the person and their parent carer to discuss what would be involved in participation in the research study. The researcher will read through the information sheet with the potential participant and their parent carer.

The verbal explanation given to the potential participant and their parent carer will be given by a member of the research group identified on the delegation log, and will cover all the elements specified on the participant information sheets and consent forms. There will be an opportunity to discuss the study and the potential participant and their parent carer will be given every opportunity to clarify points they do not understand and, if necessary, ask for more information. The participant and their parent carer will be given sufficient time to consider the information sheets provided. It will be emphasised that the participant may withdraw their consent to participate at any time without loss of benefits to which they otherwise would be entitled. When a potential participant, and their parent carer, are satisfied that all their questions have been adequately answered, he/she will be invited to choose whether or not they would like to participate.

During the process of obtaining consent, procedures in keeping with the Adults with Incapacity Act, 2000, will be used. The written consent form will use language appropriate to the developmental level of individuals with LD. Where participants are under 16, their parent carer will be required to provide their consent for them to participate in the research. Parent carers will also be providing their own consent to participate in the study. The consent form will be read through with the individual with LD and they will be asked to sign it, witnessed by a carer or other individual independent of the study. A member of the research group and the participant will sign and date the consent form to confirm that consent has been obtained. The participant will receive one original consent form, the second original will be kept in the trial master file.

Only after an individual has consented to participate will screening data be collected.

Below lists the participant information sheets and consent forms for the participant:

- 1. Simplified and accessible easy read information sheet
- 2. General information sheet
- 3. Simplified and accessible easy read consent form
- 4. General consent form

6.1.2. Carer

The main identified carer will be given the following information sheet and consent form:

- 1. General information sheet
- 2. Consent form

7.0 Withdrawal and loss to follow-up

Participants have the right to withdraw consent for participation in any aspect of the trial at any time. The participant's care will not be affected at any time by declining to participate or withdrawing from the trial. Data collected up to the point of withdrawal from the trial will still be used in the analysis, unless the participant or their parent carer, requests for their data to be removed prior to analysis taking place (date to be specified in information sheets).

8.0 Study interventions

Participants will be randomised to either:

- 1) Beat-D for depression
- 2) Treatment as usual

8.1 Beat-D

The treatment is designed to be delivered to individuals alongside a parent carer. It is a structured, time limited, manualised psychological therapy, developed to treat those with an LD and depressive symptoms. There is an initial training session for carers regarding their role in the treatment, then 8-12 sessions held 1-2 weekly, spanning approximately 4 months. The treatment can be delivered in person, or using video conferencing.

The treatment is divided into two phases, starting with an assessment period (4 sessions), where the participant with LD and their carer are socialised into the model and an individual formulation is developed. Key components of this phase include: i) identifying avoidant behaviours linked to depressive symptoms and monitoring activity, ii) identifying life goals, and iii) psycho-education concerning the link between depression and activity. The assessment culminates in the presentation of a formulation to the participant and their carer (session 4). This provides a shared 'story' or common frame of reference for joint work between the participant, carer and therapist. Maximum participation by the person with LD is achieved by flexibly implementing the sessions in accordance with the treatment manual, and the particular approach taken is based upon the psychological formulation. The shared agreement of the carer regarding the treatment goals is also essential, as otherwise they are unlikely to be properly supportive of the intervention or willing to motivate the participants to achieve change.

The subsequent 5-10 active treatment sessions focus on: (i) recovering lost skills and interests and new skills training, (ii) graded exposure to reduce avoidant behaviours, (iii) targeting inherently reinforcing activity and activity likely to increase access to other positive reinforcers in three life domains: domestic tasks, purposeful daytime activity and social/recreational activity, and iv) addressing other emotional or inter-personal barriers to change, including anxiety and anger.

The final two sessions after the active treatment phase have a future focus and are concerned with helping the participant and carer to maintain and build on progress they have made. A booklet is prepared for the participant and carer, reviewing progress and identifying changes that have been made, along with a plan for long-term maintenance and improvement.

Completion of the treatment is defined as attendance and participation in a minimum of eight sessions.

8.2 Treatment as usual

This will include the existing treatments available in NHS and social care for adolescents with LD with depression, including anti-depressants, mood stabilizers, and any available psychological interventions. Information will be collected from both groups about service supports and treatments they receive during the course of the study, to help describe treatment as usual and to inform the data collection methods for the economic element of a future trial.

8.3 Therapist adherence to the Beat-D protocols

To establish adherence in the delivery of the Beat-D treatment by therapists, fidelity checklists will be completed after every session by the therapists and provided to the research team for analysis.

8.4 Risk Assessment

Risk information regarding visiting participants at home will be communicated to researchers and therapists by the referring individual/organisation. The participant should be informed of this. If the allocated participant is not previously known to services, the therapist should follow their service's standard procedure for seeing new clients safely.

8.4.1 Lone Working Policy

A Lone Working Protocol has been created for Research Assistants carrying out home visits/assessments (Appendix A)

8.4.2 COVID-19 Mitigation

There are risks associated with the COVID-19 pandemic for this study. For the Recruitment and Consent/Screening phases, risk to either participants or the study team because of taking part in this study or carrying our any procedure associated with this study is minimal. The reason is that these phases will take place via the phone or online using video-conferencing and online survey methods.

The assessment, intervention and post intervention phases pose greater risk as there is likely to be planned contact between members of the study team, health care professionals, and parents/carers/participants. However, as this study will take place in the NHS, and will be delivered by NHS clinicians, any wider COVID-related risk mitigation strategies in operation within NHS Trusts will apply to this study, the study team, and any therapist working as part of the study. This is likely to involve the use of Personal Protective Equipment and/or increased use of video conferencing or telephone calls.

9.0 Safety Reporting

9.1 Definition of adverse event

Adverse Event (AE) – Any unfavourable and unintended sign, symptom or disease temporarily associated with participation in the study.

9.2 Definition of Serious Adverse Event

Serious Adverse Event (SAE) - Any untoward occurrence that:

Results in death

Is life-threatening [refers to an event during which the participant was at risk of death at the time of the event; it does not refer to an event which might have caused death had it been more severe in nature]

Requires hospitalisation, or prolongation of existing hospitalisation

Results in persistent/significant disability or incapacity

Is a congenital abnormality or birth defect

Is otherwise considered medically significant by the investigator

9.3 Recording and Reporting of Adverse Events

AEs will be identified by observation and/or enquiry at study visits. AEs that do not meet the criteria for seriousness will be recorded in documentation on the Case Report Form (CRF) only. Details of SAEs will be added to the CRF and followed until resolution. Expected SAEs should be followed until resolution. The relationship with the study intervention will be assessed for any unexpected SAEs. If unexpected SAEs are possibly or definitely related to the study intervention, these unexpected SAEs will be communicated to the CI for review and will be reported to the Research Ethics Committee. Unexpected and unrelated SAEs will be

followed until resolution.

9.4 Reporting to the Sponsor

All SAEs that arise during the Beat-D trial will be reported by the PI (or designee) to the CI and Sponsor by entering the details into the CRF as quickly as practicable and in any event within 24 hours upon becoming aware of the event. Any follow up information should also be reported.

9.5 Reporting to the Research Ethics Committee

Any SAE occurring to a research participant will be reported to REC (the REC that gave favourable opinion of the study) where in the opinion of the Chief Investigator, the event was

- related that is, resulted from administration of any of the research procedures, and
- unexpected that is, the type of event not listed in the protocol as an expected occurrence.

Reports of related and unexpected SAEs should be submitted to the REC within 15 days of the CI becoming aware of this event using the 'report of serious adverse event form' for non-CTIMPs published on NRES website.

9.6. Annual progress report

The CI is also responsible for providing an annual progress report to the REC using NRES 'Annual Progress Report form for all other research'. A section on the safety of participants is included in this report.

10.0 Study Outcomes

10.1 Measures/assessment instruments

As shown in Figure 1, outcome measure data will be collected at two time points:

- Baseline
- Time 1 four months post-randomisation (post intervention)

Data collection interviews should take place as close to the scheduled data collection point as possible and always within the period of between two weeks before and four weeks after the due date (based on date of randomisation).

Outcome measures for the feasibility study include:

- 1. Depressive and anxiety symptoms
- 2. Behavioural Activation and coping ability
- 3. Participant activity levels
- 4. Quality of life
- 5. Carer efficacy
- 6. Service use (information about service supports and treatments)

An outline of data collected at the two time points is shown in Table 2, below. Research interviews will take place in the home environment of participants. If participants prefer, these interviews will take place in appropriate clinical, provider organisation or charity premises. In addition to the assessments listed in Table 2, a purpose specific questionnaire to gather demographic and health data about participants will be completed at baseline only. This will include questions about the participants' expectations of therapy. This questionnaire was used in the initial Beat-It-A (for adults) clinical trial and takes 20 minutes to complete.

Carers will also be given the option to complete assessments with the researcher by phone if it proves to be more convenient for them or difficult to arrange a time to meet face to face.

Table 2: Outcome measure assessments

Outcome	Measures
Depressive symptoms	Glasgow Depression Scale for Intellectual Disabilities (20 items: 10 minutes)
	Glasgow Depression Scale for Intellectual Disabilities – Caregivers Supplement (16 items: 10 minutes)
Behavioural Activation	BADS (8 items: 10 minutes)
Anxiety symptoms	Glasgow Anxiety Scale for Intellectual Disabilities (27 items: 10 minutes)
	Spence Children's Anxiety Scale – Parent Report (45 items: 15 minutes)
Carer Self-efficacy	Emotional Difficulties Self-Efficacy Scale (10 items: 5minutes)
Quality of life	EQ-5D-Y Proxy version (5 dimensions: 5 minutes)
	EQ-5D-Y Interviewer Administered version (5 dimensions: 10 minutes)
Health economics	Client Service Receipt Inventory (30 items: 10 minutes)

10.2 Measures of depressive and anxiety symptoms

Depression symptoms

Glasgow Depression Scale¹⁷: The Glasgow Depression Scale is a self-report measure designed to assess depressive symptoms in people with LD. It consists of 20 questions assessing depressive symptoms over the past week and is designed to be easily understood and completed by individuals with mild to moderate LD. Participants (adolescents) will complete this measure at baseline and 4 months. It takes approximately 10-15 minutes to complete.

Glasgow Depression Scale – Caregiver Supplement¹⁷: The Glasgow Depression Scale – Caregiver Supplement (GDS—CS) consists of 16 items and was designed to assess carers' views and report of their direct observations and concerns about the prevalence of depressive symptomatology of the person with LD. The scale can assess symptom level across a 1-week period and can be used both as a process and an outcome measure.

Children's Depression Rating Scale Revised: The CDRS-R is a brief rating scale based on a semi-structured interview with children and adolescents. The clinician rates 17 symptom areas that are used to aide in diagnosis of depression. Each item is rated on a 7point scale, with a final Summary Score obtained. It takes approximately 15-20 minutes to complete, and will be administered at both baseline and 4 months to gather information on change in depression symptomatology.

Anxiety symptoms (self-report)

Glasgow Anxiety Scale for people with ID (GAS-ID): Self-reported measure designed to measure the intensity of anxiety symptomatology in people with an intellectual disability and has been shown to discriminate between anxious and non-anxious participants. It consists of 27 items. Takes approximately 10 mins to complete and will be completed by the adolescent themselves at baseline and 4 months.

10.3 Behavioural Activation and functional engagement with activities

Behavioural Activation for Depression Scale: The BADS is an 8-item clinician or self-administered questionnaire, designed to track changes weekly in behaviours

hypothesised to underlie depression and specifically targeted for change by behavioural activation. Has been previously used with neurotypical participants and has been adapted for adolescents with LD. It will be administered at baseline and at 4 months

10.4 Qualitative interviews and process evaluation

Carer and therapist interviews will be conducted according to a semi-structured interview schedule. The questions will address the participants' views and experiences of the Beat-D therapy and attention control to develop a better understanding of the change process. Design of the set of tools will take account of lessons learnt on our own and others' previous work, taking in the views of people with LD, including guidelines approved by the ESRC.

As a standard part of the Beat-D treatment protocol, therapists also complete written therapist logs at the end of each intervention session, noting their impressions of barriers to change, the successful therapy tasks and ways they adapted the approach (in accordance with the manual) to individual needs and circumstances.

Therapists will also collect routine data from the participants about their level of activity and their success in carrying out the homework tasks, along with reports from the participants about their mood that will provide evidence of the pattern of change across sessions.

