3.2 Secondary objectives

- 1. How acceptable is the treatment to the adolescents with LD, their parents/carers, and therapists? Do therapists feel the therapeutic processes were appropriate for adolescents and their parents/carers?
- 2. What is the rate of recruitment of adolescents with depression and mild-moderate LD to the study over a 10-month period?
- 3. What is the retention rate of the recruited adolescents with LD six-months post-randomisation?
- 4. Which outcome measures (potential primary and secondary outcome measures) have greatest utility to detect meaningful change in the participants with LD, and their parents/carers?
- 5. Are adverse events associated with the treatment in this study population?
- 6. What are the reasons for study non-completion?
- 7. Is behavioural activation delivered with fidelity to the manual/model, and what is the adherence of participants to the treatment?
- 8. What is treatment as usual for adolescents with LD and depression?

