4.0 Study design

The proposed study is a single-centre, single-blind, feasibility randomised controlled trial (RCT) of Beat-D compared to treatment as usual, plus a qualitative investigation of adolescents', carers', and therapists' perspectives on the treatment. The design of the study is illustrated in Figure 1, and the schedule of research assessments outlined in Table 1. The researchers collecting the outcome data will be blinded to which group participants have been allocated.

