12.2.2 Qualitative analysis

The interviews will be analysed using framework analysis. This is a highly structured form of qualitative data analysis initially developed by the National Centre for Social Research²⁴ and particularly suited for applied research. Rather than themes and subthemes being wholly emergent from the data, framework analysis allows the researcher to start with a set of a priori themes which are used as an initial guide to the analysis, although in the analysis these themes can be altered and new themes can emerge from the data. Framework analysis is less labour-intensive than many other types of qualitative data analysis, and allows for the systematic examination of data from relatively large samples for qualitative analysis.

For this study, the major a priori themes to begin the framework analysis will concern a number of dimensions that may inform the future uptake of the intervention in clinical practice. These will include: carers' and therapists' perspectives on the process of change; helpful and unhelpful aspects of the interventions; factors relating to the three-way working relationship and the carer-participant relationship; and

barriers and facilitative factors relating to the maintenance of the interventions after cessation of contact with the therapist.

This part of the research is not hypothesis driven. Instead, the main aim is to gain an 'insider's perspective' that will assist with the interpretation of the results and inform decision making about whether a full scale clinical trial is warranted.

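### The protocol promises adolescents' own views on the acceptability of Beat-D, but its interview procedure covers only carers and therapists and names a comparator the trial does not have

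*Protocol*

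**What the plan says.** Two sections promise three respondent groups. Secondary objective 1 in Protocol 3.2 asks "How acceptable is the treatment to the adolescents with LD, their parents/carers, and therapists". Section 4.0 sets out a "feasibility randomised controlled trial (RCT) of Beat-D compared to treatment as usual". To that comparison the same section adds an interview strand, worded as "plus a qualitative investigation of adolescents', carers', and therapists' perspectives on the treatment".

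The sections that turn this promise into procedure name two groups. Section 10.4 says "Carer and therapist interviews will be conducted according to a semi-structured interview schedule", and that the questions will address participants' "views and experiences of the Beat-D therapy and attention control to develop a better understanding of the change process". In 12.2.2 the first a priori theme is "carers' and therapists' perspectives on the process of change". The next themes name no respondent: "helpful and unhelpful aspects of the interventions; factors relating to the three-way working relationship and the carer-participant relationship".

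Table 1 schedules a qualitative interview in a sub-sample at about four months from randomisation, without saying who is interviewed.

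**The concern.** The adolescent is the person treated, and the protocol lists adolescents first among those whose judgement of the treatment it wants. If the interviews go ahead as 10.4 describes, what is known about acceptability to adolescents will come from carers and therapists. Section 12.2.2 gives the qualitative work an important role: it is meant to supply an insider's view and to inform whether a full-scale trial is warranted. For the treated group that view would be second-hand.

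The attention-control wording adds a smaller problem. An interview schedule built on that sentence would ask about a condition that nobody in this trial receives. It would not prompt carers in the treatment-as-usual group about what they did receive.

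**Working it through.** The protocol gives no figure on this point, so there is nothing to reproduce. The check is a comparison of sections.

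**1. Who is to be heard**

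| Protocol section | Adolescents | Carers | Therapists |
|---|---|---|---|
| 3.2, objective 1 | named | named | named |
| 4.0, design | named | named | named |
| 10.4, interviews | not named | named | named |
| 12.2.2, first theme | not named | named | named |
| 12.2.2, other three themes | no respondent stated | no respondent stated | no respondent stated |
| Table 1, interview column | no respondent stated | no respondent stated | no respondent stated |

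The objective and the design name three groups. The only procedure names two.

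**2. Whether another source fills the gap**

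- Table 2 and sections 10.2, 10.3 and 10.5 cover depressive and anxiety symptoms, behavioural activation, carer self-efficacy, quality of life and service use. None of these asks the adolescent how acceptable the treatment was.
- The demographic and health questionnaire (10.1) includes expectations of therapy, but only at baseline, before any treatment.
- The routine data that therapists collect from participants (10.4) concern activity, homework and mood.
- Therapist logs (10.4) and fidelity checklists (8.3) are completed by the therapist.
- The phrase "taking in the views of people with LD, including guidelines approved by the ESRC" in 10.4 describes how the tools are designed. It does not set up an interview with adolescents.
- Retention and reasons for non-completion (objectives 3 and 6) are at best indirect signs of acceptability.

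No specified source records the adolescent's own view of the treatment.

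**3. Whether the protocol gives a reason to leave adolescents out**

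It gives none. Inclusion criterion 4 (5.3) takes capacity to assent or consent as implying enough communication and understanding for the treatment. Adolescents also complete the Glasgow Depression Scale, the Glasgow Anxiety Scale and an interviewer-administered EQ-5D-Y themselves.

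**4. Comparator**

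The title and sections 4.0, 8.0 and 8.2 all give the second arm as treatment as usual. Only 10.4 mentions an attention control.

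**5. Scale**

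The target is 20 adolescents (5.1), half of them allocated to Beat-D (1.0): 20 × 1/2 = 10. Adding adolescents therefore means at most about 10 interviews on the treatment, and fewer if the sub-sample is kept.

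**The case against.** The best reply is that the protocol never excludes adolescents. Section 4.0 commits to their perspectives, Table 1 leaves the respondent open, and 10.4 refers to the views of participants. The team may well intend to interview them, with 10.4 simply worded too narrowly. This stands to the extent that it would be wrong to say adolescents have been ruled out. It does not remove the need for correction, because the section staff will work from names two groups.

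Three stronger readings are tempting, and the text does not support them.

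- *The analysis framework shuts adolescents out.* Only the first of four themes names carers and therapists. The other three could hold adolescent data, and 12.2.2 allows themes to change and new ones to emerge.
- *Those who stop treatment early will not be heard, so acceptability will look too favourable.* The interview is timed from randomisation, not from treatment completion. Section 7.0 allows withdrawal from any single aspect of the trial, so a person who stops Beat-D can still be interviewed. Nothing limits the sub-sample to completers, and the protocol gives no stopping rate from which a bias could be sized.
- *All Beat-D dyads should be interviewed.* A sub-sample is an ordinary choice in qualitative work and is not an error here.

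A practical objection concerns masking. Section 11.0 keeps the outcome assessors masked until all participants have left the trial, and talking to adolescents about Beat-D would reveal their allocation. The same is true of the carer interviews already planned, so an interviewer other than the masked assessors is needed in any case.

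The attention-control wording is a separate matter from objective 1. It is a mismatch in the same section that can be corrected in the same amendment.

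**Conclusion.** The point holds as an internal contradiction. Sections 3.2 and 4.0 promise adolescents' own perspectives, and 10.4, supported by the first theme in 12.2.2, provides for carers and therapists only. No listed measure makes up the difference. If 10.4 is carried out as written, acceptability to one of the three groups in objective 1 would rest on proxy report. The carer and therapist parts of the objective are unaffected, including its question on whether therapists found the process appropriate. So are the quantitative analyses.

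This rests on one assumption: that staff follow 10.4 literally. If adolescent interviews are already intended, the correction is one of wording only. The reference to an attention control is wrong whatever the intention. Both should be put right before the interview schedule is finalised.

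**What to change.** Amend four places.

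- **10.4, respondents:** change the opening to *Adolescent, carer and therapist interviews*.
- **10.4, comparator:** replace *attention control* with *treatment as usual*.
- **12.2.2:** add adolescents to the first a priori theme.
- **Table 1:** state who is interviewed. The sub-sample may stay, with a line saying that it is not restricted to those who completed treatment.

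The contradiction could also be removed by narrowing objective 1 and section 4.0 to carers and therapists. That would give up the treated person's view, which a feasibility study is well placed to collect.

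The cost is small: a few short interviews alongside those planned with carers, done by the carer interviewer and not by the masked outcome assessors. The amendment needs the approvals listed in 14.1 (Chief Investigator, sponsor, research ethics committee and NHS R&D).
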